24.1 Derived Variables

Total scores which are (also) calculated by the investigator (e.g. the UMSARS part I score used for inclusion/exclusion), will be represented in two variables: one calculated directly from item scores (e.g. PARAMCD: UMSARSP1) and one with the same name and the extension 'I' containing the total score as calculated by the investigator (e.g. PARAMCD: UMSARSP1).

24.1.1 Missing Item Scores

Since all rating scales will be performed electronically missing single items should in principle not occur. However, if >20% of the items for a rating scale or subscale are missing, the total score or subdomain score will be set to missing. The maximum number of missing items is given for each in Panel 6.

If number of missing items in a scale does not exceed the maximum number, total scores and/or subdomain scores will be imputed for the UMSARS part I and part II, SE-ADL, and EQ-5D-5L. The general rule when imputing total scores or subdomain scores is that the score will be calculated using the SAS function ROUND:

Study 18331A - Statistical Analysis Plan

ROUND ([(sum of scores in non-missing items) / (number of non-missing items) * (total number of items)])

Derived scores including imputed items will be marked (DTYPE = 'EXTRAP').

PARAMCD	Description	Maximum Number of Missing Items
UMSARSP1	UMSARS part I score, 12 items	2
UMSARSP2	UMSARS part II score, 14 items	2
EQ5D5L	EuroQoL 5-dimension, 5 items	1

Panel 6	Maximum	Number	of Missing	Items on	Rating Scales
---------	---------	--------	------------	----------	----------------------

An exception to this rule will be for patients dropping out due to death. In case of death, the total or domain score will be set to worst rank according to Panel 7 below at the visit following the date of death applying both a narrow and a broad visit windowing approach. Hereafter, scores will be set to missing.

In case of drop-out due to death, derived scores will be included for the imputed values marked with $D_TYPE = 'WC'$.

PARAMCD	Description	Imputed worst rank
UMSARSP1	UMSARS part I score	48
UMSARSP2	UMSARS part II score	56
UMSARSTS	UMSARS total score	104
mUMSARS	Modified UMSARS part I score	48
COMPS	COMPASS Select Change - Orthostatic Intolerance Score	-60
COMPS	COMPASS Select Change – Secretomotor Score	-25
COMPS	COMPASS Select Change – Bladder Score	-30
COMPS	COMPASS Select Change – Vasomotor Score	-10
COMPS	COMPASS Select Change – Sleep Score	-25
SEADL	Schwab & England ADL score	0%
CGIS	Clinical Global Impression score – Severity	4
PGIS	Patient Global Impression score – Severity	4
OGIS	Observer-reported Global Impression – Severity	4
EQ5D5L	EuroQoL 5-dimension, each single domain	5

Panel 7 Imputation of worst rank following events of death

24.1.2 UMSARS scale

The UMSARS scale consists of four part, i.e. part I-IV, where part I and part II are covering multiple domains with an associated score, whereas part III is covering an autonomic examination and part IV is a 1-dimensional disability scale. In addition, two moderated

UMSARS scores will be derived, i.e., a modified UMSARS part I (mUMSARS) score and an abbreviated UMSARS (aUMSARS) score, respectively.

	UMSARS	Total Score		
	PART 1	PART 2	PART 3	PART 4
Historical functional review of activities of daily living over the past two weeks		Motor examination scale	Autonomic examination (supine blood pressure after	
1. 2. 3. 4. 5. 6. 7. 8. 9. 10. 11. 12.	Speech Swallowing Handwriting Cutting food/handling utensils Dressing Hygiene Walking Falling (past month) Orthostatic symptoms Urinary function Sexual function Bowel function	1. Facial expression 2. Speech 3. Ocular motor dysfunction 4. Tremor at rest 5. Action tremor 6. Increased tone 7. Rapid alternating hand movements 8. Finger taps 9. Leg agility 10. Heel-knee-shin test 11. Arising from chair 12. Posture 13. Body sway 14. Gait	15 min rest, and standing blood pressure within 10 mins of standing, supine and standing heart rate, and presence of autonomic symptoms)	Global disability scale, ranging from 1 (completely independent) to 5 (totally independent)
	Scored from 0-104	, with higher scores ater impairment		

Panel 8 UMSARS Scale Overview

UMSARS part I and mUMSARS

The UMSARS part I comprises 12 items rating the average functional situation for the past 2 weeks (unless specified) according to the patient and caregiver interview. It covers the following domains: speech, swallowing, handwriting, cutting food and handling utensils, dressing, hygiene, walking, falling, orthostatic symptoms, urinary function, sexual function, and bowel function; all rated 0 to 4, with 0 = not affected/normal; 1= mildly affected/ impaired; 2= moderately affected/impaired; 3= severely affected/impaired; and 4 = helpless or entirely affected/impaired. The UMSARS part I total score ranges from 0 to 48.

If more than 2 items for the UMSARS part I are missing, the score will be set to missing. If no more than 2 items are missing, the score will be equal to the mean of the recorded items multiplied by the total number of items and then rounded to the first decimal place using the SAS function ROUND:

ROUND ([(sum of scores in non-missing items) / (number of non-missing items) * (total number of items)]).

The modified UMSARS part I (mUMSARS) score is derived by collapsing the response option 0 and 1 within each item $\{0 \& 1 = 1\}$. Hence, the mUMSARS score ranges from 12 to 48. In case of missing items the same above rule will be applied using the ROUND function.

UMSARS part II

The UMSARS part II comprises 14 items rating different aspects of motor performance for the worst affected limb at the actual visit. It covers the following domains: Facial expression, speech, ocular motor dysfunction, tremor at rest, action tremor, increased tone, rapid alternating movements of hands, finger taps, leg agility, heel-knee-shin test, arising from chair, posture, body sway, gait; all rated 0 to 4, with 0 = not affected/normal; 1= mildly affected/ impaired; 2= moderately affected/impaired; 3= severely affected/impaired; and 4 = helpless or entirely affected/impaired. The UMSARS part II total score ranges from 0 to 56.

If more than 2 items for the UMSARS part II are missing, the score will be set to missing. If no more than 2 items are missing, the score will be equal to the mean of the recorded items multiplied by the total number of items and then rounded to the first decimal place using the SAS function ROUND:

ROUND ([(sum of scores in non-missing items) / (number of non-missing items) * (total number of items)]).

UMSARS part III

The UMSARS part III comprises an autonomic examination of systolic blood pressure, diastolic blood pressure, heart rate, and orthostatic symptoms. Supine blood pressure and heart rate are measured after 2 minutes of rest and again after 2 minutes of standing. Orthostatic symptoms are assessed as 'yes'/'no' and may include lightheadedness, dizziness, blurred vision, weakness, fatigue, cognitive impairment, nausea, palpitations, tremulousness, headache, neck and "coat-hanger" ache. The UMSARS part III is not reported as a joint score.

Missing data from UMSARS part III will not be imputed.

UMSARS part IV

The UMSARS part IV comprises a global disability scale ranging from 1-5, with 1='Completely independent. Able to do all chores with minimal difficulty or impairment. Essentially normal. Unaware of any difficulty'; 2='Not completely independent. Needs help with some chores'; 3='More dependent. Help with half of chores. Spends a large part of the day with chores'; 4='Very dependent. Now and then does a few chores alone or begins alone. Much help needed'; and 5='Totally dependent and helpless. Bedridden'.

Missing data from UMSARS part IV will not be imputed.

The UMSARS TS is derived as the sum of part I and part II, hence ranging from 0 to 104. The UMSARS TS will be missing in case either part I or part II would be missing at the same visit.

The UMSARS subscale scores are described in Panel 9.

UMSARS total score and domain scores	Derivation	Range	
UMSARS part I	Sum of part I items (1.1-1.12)	0-48	
UMSARS part II	Sum of part items (2.1-2.14)	0-56	
UMSARS part III	Individual part III items (3.1-3.4)	NA	
UMSARS part IV	One item score 4.1	1-5	
UMSARS TS	Sum of part I and part II	0-104	
Modified UMSARS (mUMSARS)	Sum of part I items with response option 0 and 1 collapsed (=1)	12-48	
Abbreviated UMSARS (aUMSARS)	Sum of part I and part II selected items	0-40	
* since the abbreviated UMSARS is still under development the final items will be amended at a later point.			

Panel 9 Derivation of UMSARS total score and domain scores

24.1.3 Composite Autonomic Symptom Score Select (COMPASS Select)

The COMPASS 31 is a refined, internally consistent, and markedly abbreviated quantitative measure of autonomic symptoms. It provides clinically relevant scores of autonomic symptom severity based on the well-established 169-item Autonomic Symptom Profile (ASP) and its validated 84-question scoring instrument, the Composite Autonomic Symptom Score (COMPASS). However, it applies a much-simplified scoring algorithm, and is suitable for widespread use in autonomic research and practice. COMPASS Select is a simplified version of the COMPASS 31 with selected items only.

Two versions of the COMPASS Select will be applied. At baseline, the COMPASS Select which is a 36-item questionnaire asking into autonomic symptoms within the past year. At subsequent visits, the COMPASS Select Change which is a 16-item questionnaire asking into changes in symptoms since last evaluation.

Since the COMPASS Select Change is licenced by the Mayo Clinic, they will be responsible for deriving the total scores to be used for further analysis. Patient-level single item data and the derived score will be included in sdtm format.

COMPASS Change Select Domain*	Questions in domain	Range**
Orthostatic Intolerance domain Score (OI_domain)	Q1, 2, 3, 4, 5, 6	-60-60
Secretomotor domain score (Secretomotor_domain)	Q10, 11, 12	-25-25
Bladder domain score (Bladder_domain)	Q7, 8, 9	-30-30
Vasomotor domain score (Vasomotor_domain)	Q13	-10-10
Sleep domain score (Sleep_domain)	Q14, 15, 16	-25-25
COMPASS Change Select score (COMPASS_Change_Select)	Sum of all 5 domains	-150-150
* COMPASS Select Change domain scores will be deri	ved by Mayo Clinic	

Panel 10 **COMPASS Select Change domain scores**

** the lower score the more severe symptoms

24.1.4 Schwab & England Activity Daily Living Scale (SE-ADL)

The Schwab and England Activities of Daily Living (SE-ADL) scale is a method of assessing the capabilities of people suffering from impaired mobility. Originally presented at a Parkinson's disease conference, the scale assesses the difficulties patients have completing daily activities or chores. The scale uses percentages to represent how much effort and dependence on others, patients need to complete daily chores. The rating may be given by a professional or by the person being tested. Only the clinician reported part will be included in this study.

Percentage of independence	Degree of independence	Description
100%	Completely independent	Able to do all chores without slowness, difficulty or impairment.
90%	Completely independent	Able to do all chores, but with some degree of slowness, difficulty and/or impairment. One might take two times longer than normal to complete chores.
80%	Usually completely independent	Takes two times longer than normal to complete chores.
70%	Mostly independent	Faces more difficulty with some chores. One spends a large part of the day with chores and might take three to four times longer than normal.
60%	Somewhat independent	Can do most chores, but exceedingly slowly and with much effort. Errors are possible during the chores.
50%	Mostly dependent	Needs help with half of every chore. Everything is difficult to one.
40%	Very dependent	Can assist with chores and can complete some alone.

Percentage of independence	Degree of independence	Description
30%	Very dependent	With help, can start chores. One can also complete few chores with effort and help.
20%	Very dependent	Can slightly help with chores but cannot complete any alone.
10%	Fully dependent	Is helpless and somewhat comatose.
0%	Fully dependent	Is bedridden and helpless. One is almost completely comatose.

24.1.5 Clinical Global Impression Severity Scale (CGI-S)

The CGI-S is administered by an experienced neurologist familiar with MSA patients to make an expert clinical global judgement about the severity of the disease across various time points. The neurologist makes a judgement about the total picture of the patient at each visit: the disease severity, the patient's level of distress and other aspects of impairment, and the impact of disease on functioning. The rating is based upon observed and reported symptoms, behaviour, and function in the past seven days. Symptoms and behaviour may fluctuate over a week; the score should therefore reflect the average severity level across the seven days. The CGI-S is rated on a scale ranging from 0 to 4 (whereas the 0 = normal, not impaired; 1 =mildly impaired; 2 = moderately impaired; 3 = severely impaired; 4 = extremely impaired).

24.1.6 Patient global Impression Scale (PGI-S)

The PGI-S is a self-reported single item to evaluate all aspects of patients' MSA symptoms. Patients are asked to choose the response that best describes the severity of their MSA symptoms over the past week. The question is rated on a 5-point scale ranging from 0 to 4 (0 = none; 1 = minor; 2 = moderate; 3 = severe; 4 = very severe). It takes approximately 1 minute to complete the PGI-S.

24.1.7 Observer-reported Global Impression – Severity of Illness (OGI-S)

The OGI-S is a single-question carer/observer-reported outcome to evaluate all aspects of patients' MSA symptoms. Carer/observers are asked to choose the response that best describes the observed severity of MSA symptoms in the person they care for over the past week. The question is rated on a 5-point scale ranging from 0 to 4 (0 =none; 1 =minor; 2 = moderate; 3 = severe; 4 = very severe). It takes approximately 1 minute to complete the OGI-S.

24.1.8 EuroQoL five-dimensional five-levels Scale (EQ-5D-5L)

The EQ-5D instrument comprises a short descriptive system questionnaire and a visual analogue scale (EQ VAS) that are cognitively undemanding, taking only a few minutes to complete. The questionnaire provides a simple descriptive profile of a respondent's health state. The EQ VAS provides an alternative way to elicit an individual's rating of their own overall current health. When the descriptive system profile is linked to a 'value set', a single

summary index value for health status is derived that can be used in economic evaluations of healthcare interventions.

The EQ-5D-5L covers five domains (i.e. MOBILITY, SELF-CARE, USUAL ACTIVITIES, PAIN / DISCOMFORT and ANXIETY / DEPRESSION) all evaluated using 5 response levels: 'having no problems', 'having slight problems', 'having moderate problems', 'having severe problems' and 'being unable to do/having extreme problems'.

Responses are coded as single-digit numbers expressing the severity level selected in each dimension. For instance, 'slight problems' (e.g. 'I have slight problems in walking about') is always coded as '2'. The digits for the five dimensions can be combined in a 5-digit code that describes the respondent's health state; for instance, 21111 means slight problems in the mobility dimension and no problems in any of the other dimensions. An EQ-5D summary index is derived by applying a formula that attaches values (weights) to each of the levels in each dimension. The index is calculated by deducting the appropriate weights from 1, the value for full health (i.e. state 11111).

The EQ VAS records the respondent's overall current health on a vertical visual analogue scale, where the endpoints are labelled 'The best health you can imagine' and 'The worst health you can imagine'.

24.1.9 FeetMe® gait parameters

The FeetMe® Monitor sole combines pressure sensors, inertial control units and on-board computing capacity for real-time measurement of walking parameters and plantar pressures, which will be applied periodically for a subgroup according to study procedure (See Appendix IV). The patients receive insoles during scheduled visits and are asked to wear the insoles continuously for 10 days in their home environment in the 5 pre-defined periods (baseline and 4 post-dose assessments).

Equipped with inertial units and plantar pressure sensors, the soles provide quantitative and real time readings of the following gait parameters: heel attack, heel lift, swing duration and duration, single and double support, oscillation time, distance and walking speed, cadence, plantar pressure peak map. These parameters are measured on both feet and thus provide the asymmetries relative to these parameters.

Individual parameters of gait will be derived by-step for each home-based assessment period. For analysis purpose, parameters will be further collapsed using both the median and the 95th percentiles for each day and period, respectively. Additional percentiles will be derived for exploratory purposes. Panel 12 below contains a list of available parameters and endpoint description.

Technology	Parameter	Unit	Endpoint Description
FeetMe® insoles	Gait velocity	m/s	- The median and the 95 th percentiles for all gait parameters will be derived for each
	Stride length	m	 subject and home-based period For exploratory purpose, the 95th, the 75th and the 50th percentiles (median) will be
	Stride duration	S	derived on an hourly basis for all home- based gait parameters
	Swing duration	S	
	Stance duration	S	
	Cadence	steps/min	
	Distance travelled per hour	m	

Panel 12 Derivation of gait parameters, by-step

FeetMe parameters calculated at each stride: strideLength (m), widthMotion (m), timeHeelStrike1 (ms), timeHeelStrike2 (ms), timeToeOff (ms), strideDuration (ms), velocity (m/s), cadence (stride/min), swingDuration (ms), stanceDuration (ms), swingPercentage (%), stancePercentage (%), stepTime (ms), stepLength (m), asymmetryParamStepTime (ms), asymmetryParamStepLength (m), singleSupportDuration (ms), doubleSupportDuration (ms), singleSupportPercentage (%), doubleSupportPercentage (%), asymmetryParamStrideDuration (ms), asymmetryParamStrideLength (m), asymmetryParamSingleSupportPercentage (%), strideElevation(cm), Capacitive measures of the 18 pressure sensors (in atmel unity), Centers of pressure (in cm, to confirm)

In case of large amount of missing data for a subject within a given period consisting of 10 days, the percentiles will not be derived and hence these will be set to missing. Data cleaning, population classification and confirmation of decision rules for derivation of percentiles will take place prior to database lock and will be documented as part of the classification meeting.

Additionally, raw data will be made available as sdtm format.

24.1.10 BioSensics[™] PAMSys sensor

PAMSys (Physical activity and posture) is a clinical-grade wearable sensor for continuous remote monitoring of physical activity, sleep, posture, gait parameters and falls, which will be applied periodically for a subgroup according to study procedure (See Appendix IV).

Panel 13 below contains a list of available parameters and endpoint description.

Posture and postural transition	Gait parameters
 Posture classification (sitting, standing, walking and lying down) Postural transition (duration and number of occurrence) Sedentary behavior 	 Number of steps (for example per hour) Walking duration (for example per hour) Time stamp of individual steps Cadence Cadence variability Number of episodes of walking (for example per day) Number of steps per walking episode
Sleep and sleep quality	Falls and fall risk
 Start- and end-time of periods of lying down Sleep onset latency (i.e., time lying down before sleep onset) Wake time after sleep onset Total sleep time 	 Falls (number of falls and time of occurrence) Continuous fall risk monitoring

Panel 13 Derivation of PAMSys parameters

In case of large amount of missing data for a subject within a given period, endpoints might not be derived according to BioSensics procedure and hence the data will be set to missing. Data cleaning and classification will take place prior to database lock.

Additionally, raw data will be made available as sdtm format.

24.1.11 Fall Diary

Assessment of falls during the course the trial will be done using a dedicated MSA fall diary developed by Lundbeck. The diary consists of 12 questions with response options as seen below in Panel 14, with number of falls within the last 24 hours (Q2) being the key outcome for further analysis.

Question 10, 11 and 12 are only to be filled out on a weekly basis and should only occur once a week in the e-diary. However, due to an initial mistake in the set-up, the weekly questions appeared daily and hence several assessments will be available within the same week. In those cases, the Day 7 assessment (related to the Day 1 being the first day an individual fills out the diary within a period) will be the applicable one used for the analysis; meaning that remaining assessments within the same period will be disregarded. The e-diary will be updated and hence this rule will only apply for early patients having multiple entries for the weekly questions within the same week.

Fall Diary question	Specific wording	Response option
Q1	Did you fall in the past 24 hours? (A fall is defined as UNEXPECTANTLY coming to rest on the ground, floor or just a lower level than where you started.)	Yes/No
Q2	How many times did you fall in the past 24 hours?	Number
Q3	What time did you fall?	Time point
Q4	Where were you when you fell?	Indoors / Outdoors
Q5	Was it in a place you know well?	Yes/No
Q6	Did you experience any dizziness, light-headedness, feeling faint or blurred vision before falling?	Yes/No
Q7	Did you experience freezing of gait/movement locking before falling? (Freezing of gait: feeling like your feet were stuck to the ground)	Yes/No
Q8	Did you need somebody's help to get up after you fell?	Yes/No
Q9	Did the fall cause any physical injury?	Yes/No
Q10	During the last week, how many times did you consult a healthcare professional due to a fall? (consider any past falls / whenever the fall happened)	Number
Q11	During the last week, how many times did you visit a hospital due to a fall? (consider any past falls / whenever the fall happened)	Number
Q12	During the last week, how many times did you have an x-ray due to a fall? (consider any past falls / whenever the fall happened)	Number

Panel 14 Derivation of Fall Diary parameters

Number of falls per period

Within each dispense/observation period (BL, V9, V12, V15, and V18) the defined visit windows will be applied to identify valid data entries. Within each period, the total number of falls will be calculated as the sum of the Q2 responses. In addition, an adjusted total number of falls per period will be calculated as the total number of falls divided by the number of days where the Fall Diary was filled out (Q1 NOT missing). The adjusted number of falls per period will be the primary endpoint for further analysis of falls.

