# 10.2.1.8 MSA Fall Diary

At the Randomization Visit, all patients will be provisioned and trained on an electronic MSA Fall Diary. During the study patients will be instructed to record fall events on a daily basis using a MSA Fall Diary during 5 distinct intervals; 2 weeks between Randomization Visit and Baseline Visit and 4 intervals of 4 weeks during the DBP. Patients are asked to report date/time of falls (yes/no), location of the fall (indoors or outdoors, familiar or unfamiliar environment), cause of fall (experience of orthostatic symptoms or freezing of gait), action

taken, and type of injury sustained (if any). At the end of each week patients will also be asked to report any health care professional visits and hospital visits and type of examination (for example, X-ray due to the fall etc.). The use of the fall diary does not apply to a patient who scores 4 on UMSARS Part I item 7 (walking) or if the patient is wheelchair bound for unrelated disorders. This needs to be evaluated at each visit, where the fall diary is to be dispensed.

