In addition, concomitant medications continued or started after first dose of IMP will classified into two overall groups depending on purpose, i.e., treatment of motor symptoms ('anti-Parkinson medication') and treatment of autonomic dysfunction ('Autonomic dysfunction medication'). The classification will be done prior to unblinding according to Protocol Appendix VII.

The tables will be based on the APTS.

10 Exposure

For each infusion visit, information related to infusion completed as planned (yes/no), infusion temporarily interrupted (yes/no), and infusion lasted longer than 30 (+10) minutes (yes/no), as well as descriptive statistics for the duration of infusions (this duration includes duration of any infusion interruptions) and duration of temporary interruptions will be summarized by treatment group for the DB-Period and the OLE-Period, respectively.

Patients, who at any point during the study received a different dose than what was planned, will be listed for each period. The listing will include date of infusion visit, planned dose for the patient and actual dose received for the patient.

Exposure (days) to IMP will be calculated as:

(Date of last dose + 28 days) – Date of first dose + 1

Exposure to IMP will be summarized in weeks using descriptive statistics.

Study 18331A - Statistical Analysis Plan

Patient years of exposure (PYE) will be calculated as the sum of the number of days of exposure to IMP for each patient, divided by 365.25 days.

The number and percentage of patients with different durations of exposure (≤ 4 weeks, >4 to ≤ 8 weeks, >8 to ≤ 12 weeks, ..., >68 to ≤ 72 weeks) will be presented.

Exposure will be summarized based on the APTS. In addition, all infusion data will be listed.

11 Fall Diary Compliance

The Fall Diary is planned to be dispensed and filled out in 5 periods during the study, i.e., at a two-week Baseline period and at four post-baseline four-week periods, respectively. For each period, days where the fall diary has been missed will be summarized and presented by period and treatment group. Furthermore, the number of patients missing 7 days or more (at Baseline and at subsequent periods) and 14 days or more (at subsequent periods) in each period will be presented by period and treatment group.

A day where the fall diary has been missed is defined as a day where the subject did not fill out anything in the diary.

The summaries will be based on the FAS.

12 Wearable Compliance

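### The repair for the fall-diary set-up error removes duplicates per period instead of per week, so as written it discards valid weekly answers to Q10–Q12 from patients on the faulty diary

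*SAP*

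**What the plan says.** SAP 24.1.11 sets the intended frequency: "Question 10, 11 and 12 are only to be filled out on a weekly basis and should only occur once a week". Protocol 10.2.1.8 agrees: "At the end of each week patients will also be asked to report any health care professional visits and hospital visits". All three items ask about the preceding week.

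The SAP then describes the error: "the weekly questions appeared daily and hence several assessments will be available within the same week". The answer to be kept is "the Day 7 assessment (related to the Day 1 being the first day an individual fills out the diary within a period", "meaning that remaining assessments within the same period will be disregarded". On scope it says that "this rule will only apply for early patients having multiple entries for the weekly questions within the same week", because the e-diary will be updated.

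SAP chapter 11 gives the diary schedule: "at a two-week Baseline period and at four post-baseline four-week periods".

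Consequence of falls belongs to a secondary endpoint, change from baseline to Week 48 (SAP 4.3; Protocol Panel 4). SAP 14.4.2 analyses cause and consequence descriptively. SAP 24.1.11 defines a period total and a per-day adjustment for the number of falls (Q2) only. It defines no period summary for Q10–Q12.

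**The concern.** The fault is duplication within a week, but the repair works on the period. A period has only one Day 7 when days are counted from its first diary day, so one answer survives and everything else in the period goes. That includes the answers that close the later weeks, which were collected and are valid.

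Three things follow if the text is programmed as written:

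- Affected patients lose most of their Q10–Q12 data.
- Coverage depends on which diary version was in use. It therefore differs between early and late patients, and can differ between two periods of the same patient, which enters the change from baseline.
- No fallback is given if the Day 7 entry is missing. SAP chapter 11 plans to count patients who miss 7 or more, or 14 or more, diary days in a period, so missed days are expected. One missed Day 7 empties the whole period for these items.

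**Working it through.** The documents give no figure for Q10–Q12 to reproduce, so the check is a count of answers followed by an illustration.

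**Inputs.** One answer per week (SAP 24.1.11; Protocol 10.2.1.8). One baseline period of 2 weeks and four later periods of 4 weeks (SAP chapter 11; Panel 21).

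**Planned weekly answers.** 2 + 4 × 4 = 18.

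**Kept by the rule as written.** One per affected period:

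| Period | Planned | Kept | Lost |
|---|---|---|---|
| Baseline | 2 | 1 | 1 (50%) |
| Each 4-week period | 4 | 1 | 3 (75%) |
| All five periods affected | 18 | 5 | 13 (13/18 = 72%) |

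At baseline only week 2 is lost. In each later period weeks 2 to 4 are lost.

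**Kept by a per-week rule.** Days 7 and 14 at baseline, and Days 7, 14, 21 and 28 later: 2 + 4 × 4 = 18, the planned number. Each answer looks back one week, so these days cover consecutive 7-day windows without overlap.

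**What it could do to a summary.** The SAP names none for Q10–Q12, so three are considered. The event rate is an assumption, taken as constant (Poisson) at 0.02 to 0.5 per week, because the documents give no rate.

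1. *Any event in a 4-week period.* The probability is 1 − exp(−rate × weeks kept):

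| Assumed rate per week | 1 week kept | 4 weeks kept |
|---|---|---|
| 0.02 | 2.0% | 7.7% |
| 0.1 | 9.5% | 33.0% |
| 0.5 | 39.3% | 86.5% |

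2. *Total over a 4-week period.* The expected total is rate × weeks kept, so an affected period shows one quarter of an unaffected one at any rate.

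3. *Mean per answered week.* The expected value is the same for both diary versions. The standard error for an affected 4-week period is √4 = 2 times that of an unaffected one.

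**The case against.** **The wording may be a slip.** The same paragraph describes the duplication as lying within a week, both before and after the rule. A per-week rule with *period* written loosely is plausible. This stands as a reading of intent, but a programmer following the sentence would still delete valid answers, so the text needs correcting either way.

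**A reader might infer a fourfold false rise from baseline to Week 48** in a patient whose diary was corrected in between (one week kept, then four). The documents do not support that as a consequence of the plan. It requires Q10–Q12 to be summed over periods, which the SAP does not specify. Even with a correct diary, sums would cover 2 weeks at baseline and 4 at Week 48, a factor of 4/2 = 2, so only the other factor of 2 comes from the rule. A patient affected at both times has one week against one week.

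**A reader might infer bias in the treatment comparison.** None is shown. The rule depends on diary version, not on arm, in a randomised double-blind trial. Chance imbalance is possible with 40 and 20 patients, but the number affected is not stated.

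**A reader might infer that the falls endpoint as a whole is damaged.** It is not. Q2, the key diary outcome, is untouched, as are the daily items on cause (Q6, Q7), help needed to get up (Q8) and injury (Q9). Falls meeting a seriousness criterion are also reported as SAEs (Protocol 11.1.1).

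**Period length varies** (SAP 24.2.7), so a Day 28 answer is not guaranteed and 18 is a planned maximum. This is correct, and the fix allows for it.

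**Conclusion.** The concern holds as a defect in a stated data-handling rule. Read literally, SAP 24.1.11 discards 3 of 4 planned weekly answers in each affected 4-week period and 1 of 2 at baseline. It leaves nothing for a period in which Day 7 was missed.

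The consequence is lost precision and coverage that differs by diary version, confined to three descriptive items of one secondary endpoint. Period totals or any-event percentages from affected and unaffected periods would not be comparable. A mean per answered week would be comparable in expectation but less precise. The primary and key secondary endpoints are unaffected.

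The counts rest on the planned period lengths and the literal text. The event probabilities rest on assumed rates. The trial-level impact cannot be sized because the number of affected patients and periods is not given. The change is still worth making because the data exist and the repair is cheap.

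**What to change.** In SAP 24.1.11:

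1. Replace *period* with *week* in the disregard rule. For periods recorded on the faulty diary, keep the Q10–Q12 answers that close each 7-day block (Days 7, 14, 21 and 28 where available; Days 7 and 14 at baseline) and drop only the other entries of the same week.
2. Pre-specify one fallback for a missing block-end day, chosen so that its recall window does not overlap the adjacent one. Otherwise an event could be counted twice.
3. Summarise Q10–Q12 per completed weekly answer. This puts both diary versions on one scale, and also the 2-week and 4-week periods, which would not match as totals even without the error.

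It would also help to report how many patients and periods were recorded on the faulty diary, by arm.

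The cost is a few sentences in the SAP and a few lines of derivation code, settled before unblinding. No new data are needed.
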